6.1. Guided Imagery Relaxation Tape

Participants will listen to a modified Chinese language version of a guided imagery meditation tape designed for breastfeeding mothers (23). Previous randomised controlled trials have shown efficacy for this relaxation method on reducing stress and anxiety among breastfeeding mothers (4, 24). The tape will be translated into Chinese. Moreover, since the original content of this tape is designed for women who are breastfeeding their infants, while the subjects in the present study are students without breastfeeding, the tape will also be modified by cut down the breastfeeding-related content to adapt to our sample. The duration of this tape will be cut down to about 10 minutes by removing the parts specific to breastfeeding.

6.2. Music Tape

Participants will select music from the following two music lists: 1) traditional Chinese classical music (played by classical Chinese instruments), which has been traditionally used in China for patients with depression or chronic pain; 2) New-age music, a popular style that is often used for relaxation, which often draws on images of nature, the desert, the sea, and other naturescapes. These tracks are enhanced by electronic or computer-generated sounds. Since the music is created or enhanced through electronic means, the underlying rhythm and pulse can be manipulated to create a surging or pulsing effect to induce a relaxation response (25). Studies indicate that the effectiveness of music therapy on relaxation will be affected by personal preference. Hence, to enhance the effect of music therapy for relaxation, we will use the selection method to achieve a more individualized music experience for all participants.

6.3. Relaxation lighting

Compared to bright light therapy and blue light therapy which mostly show effects on people with depression, the light technique used in this study will be designed to induce relaxation. The Philips Hue system will be used. Previous studies evaluating the effects of environmental intervention on mood show that certain aspects of the imaging environment could be effective for pleasantness control (26). Clinical research also indicates that colourful ambient lighting has been shown to improve patient satisfaction and reduce pain ratings (27). Moreover, based on the research from Philips, which evaluated the feedback from patients and their staff, the colour preference of lighting may be cultural with people. Results show that people in Singapore preferring cool blue as more relaxing colour, whereas Germans preferring the warm orange. In the present study, participants will be asked to select either the “Relax”, “Energize” or “Concentrate” settings using the Philips Hue bulb, which correspond to orange, blue, and light cream respectively. The intensity of the light will be fixed.

6.4. Guided relaxation tape with relaxation lighting and music with lighting

Previous research compared the effects of guided imagery (verbal protocol) and verbal protocol with background music (24) and found that participants using the verbal protocol with background music

reported lower relaxation compared to the verbal protocol only group. The authors proposed that this might be due to confusion during the intervention when both verbal sounds and background music were experienced by participants. Therefore, in this study, we aim to evaluate the effectiveness of guided relaxation meditation with relaxation lighting as well as the music therapy with relaxation lighting, to find out whether the combined treatment could increase the relaxation level by stimulating vision (lighting) and audition (tape) together. It can be hypothesised that the effects of this combination therapy might be enhanced since the light and sounds will affect the HPA axis through different pathways.

7. Outcome measurements

Primary outcomes of this study will be perceived relaxation level, HR, BP and FT, while the secondary outcomes will be the perceptions and feeling about each treatment, including general satisfaction, perceived effectiveness, and likelihood of wanting to use the intervention in future. Evaluation will base on the design and content of the relaxation technique.

The HR, BP and FT will be measured at both the start and the end of the experiment. An automatic BP machine will be used for the measurements of HR and BP. The BP will be measured three times and the mean of three will be calculated and recorded. A thermometer will be used for the FT measurement. For the evaluation of levels of relaxation and feelings of each intervention, a visual analogue scale will be employed at the beginning and end of each intervention.

8. Statistical Analysis

Data will be analysed using SPSS 24.0. Paired t-test will be used to detect changes in each of the primary outcomes before and after the treatment. One-way ANOVA will be conducted to find differences between control and each intervention group. Post-hoc analysis will be used to compare the effectiveness of each treatment. Differences will be considered statistically significant at $p<0.05$.

9. Ethical Consideration

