This pilot study aims to find the most effective relaxation technique to help mothers who are firstly breastfeeding their infant. Hence, we will evaluate the effects of five different relaxation techniques on physical and psychological changes in Chinese mothers who are firstly breastfeeding their infant. The ultimate aim of this study is to select the most appropriate therapies for breastfeeding mothers to be used in a subsequent trial investigating the impact of relaxation theory on breastfeeding outcomes in mothers who deliver a late preterm infant. Five types of intervention used in this study include: guided relaxation meditation tape, music tape, relaxation lighting, combined relaxation meditation and lighting, and combined music and lighting.

2. Objectives

To compare and evaluate the impact of five relaxation interventions on changes of heart rate (HR), blood pressure (BP), fingertip temperature (FT) and level of relaxation among Chinese breastfeeding women. Additionally, participants' perceptions and feelings about each relaxation technique will also be evaluated.

3. Hypotheses

Primary: Compared to the control state, all five relaxation interventions associated with increased perceived relaxation in varying degrees and reduced perceived stress.

Secondary: The two combination treatments (guided relaxation tape with relaxation lighting, and music tape with relaxation lighting) might show more effectiveness than other three treatments.

4. Study Design

The present study will be conducted at Beijing Children Hospital, Beijing, China. A within-subject design will be used to evaluate the effectiveness and participants' feeling towards the five tested interventions compared to a control situation.

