4.3 Eligibility criteria

Inclusion Criteria	Exclusion Criteria
Women (primips) who are exclusively breast feeding their infants	Women who are breastfeeding their second infant and have previous experience of breastfeeding for their first infant
Between 1 month to 4 months after delivery and stay at home	After 3 months of delivery and back to the work place
Generally healthy	Women who have mastitis, or any condition that may affect breastfeeding, blood pressure, heart rate, energy expenditure, hearing ability or vision
18-45 years of age	Smokers
	Did not attend any other clinical trials within the latest 12 months

5. Study Procedures

After obtaining informed consent, all participants enrolled in this study will be asked to attend for 30 minutes once to three times per week for five relaxation treatments and one control (no treatment). The emotions and feelings of participants in both intervention and control treatment will be assessed before and after each treatment or control.

The duration of this study is six weeks. In order to fit with the subject's schedule and control the circadian rhythm, all treatments and control sessions will take place on different days each week. Each participant can choose a 30-minute time slot to fit their timetable. To make the outcome assessment more consistent, participants are encouraged to come at the same time of the day they chose. The order of interventions will be randomly assigned for each participant. Both relaxation interventions and control will be conducted in the breastfeeding room located at Beijing Children Hospital. This room is private, quiet and has comfy seating. Participants will be asked to leave their personal belongings, including any electronic devices, books and magazines, and personal work, during the experiment period.

6. Treatment of Subjects

A total of five interventions will be used in this study, in which, three basic interventions are: guided relaxation meditation tape, music tape, and relaxation lighting (Philips Hue). Moreover, since we hypothesise that a potential larger effect might be observed when using combined relaxation interventions to stimulate different senses (vision and audition) at the same time, we combined the guided relaxation tape with lighting and the music tape with lighting as two additional interventions in this study. All participants will receive all five treatments and control in random order.

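### The primary outcomes are tested first by uncontrolled before-after t-tests although the primary hypothesis is against control, and the control comparison is not named as the deciding test

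*Protocol*

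**What the plan says.** The primary hypothesis (section 3) is comparative: "Compared to the control state, all five relaxation interventions associated with increased perceived relaxation in varying degrees and reduced perceived stress". Section 4 describes the design in the same terms: "A within-subject design will be used to evaluate the effectiveness and participants' feeling towards the five tested interventions compared to a control situation". Section 6 adds: "All participants will receive all five treatments and control in random order".

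Section 8 lists three steps at a common 5% level. The first is "Paired t-test will be used to detect changes in each of the primary outcomes before and after the treatment". The second is "One-way ANOVA will be conducted to find differences between control and each intervention group". The third is an unspecified post-hoc analysis comparing the treatments. Only the first step mentions the primary outcomes by name. None is designated as the test of the primary hypothesis, and the dependent variable of the ANOVA (post-session value or change) is not given.

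On the setting, section 5 places interventions and control in one room: "This room is private, quiet and has comfy seating". On measurement, it says: "The emotions and feelings of participants in both intervention and control treatment will be assessed before and after each treatment or control". Section 7 confirms a visual analogue scale at both ends of each intervention. For heart rate (HR), blood pressure (BP) and fingertip temperature (FT), section 7 gives two time points defined by the experiment and does not mention sessions.

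**The concern.** A before-after test within one condition asks whether the outcome moved during the session. It cannot say whether the technique moved it. A woman who sits comfortably in a quiet, private room, with her devices, reading matter and work put aside, may relax whatever is played or lit. The control session exists to measure that shift, and the paired t-test does not use it. Running the same test in the control session as well would not help, because seeing which conditions reach p<0.05 is not a comparison between them.

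The stakes follow from the stated purpose, which is to choose therapies for a later trial in mothers of late preterm infants. A test that several techniques can pass through rest alone does not discriminate between them. With three analyses at the same level and none ranked, nothing in section 8 prevents a before-after result from being reported as the answer to the primary hypothesis.

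**Working it through.** **The plan's own figure.** Section 4.2 uses a mean change of 0.75 and an SD of 1.00. The printed formula gives 16 × 1.00 / 0.75² = 28.4, in line with the stated 28 per group. The within-subject figure of 14 is reproduced by (1.96 + 0.84)² × 1.00² / 0.75² ≈ 13.95, if 1.00 is the SD of the paired difference. Planned enrolment is 15 to 20.

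**Before-after test of a technique equal to control.** Let rest shift the outcome by d SDs of the change score. The two-sided paired t-test at 5% (sidedness is assumed) rejects with probability P(|T| > t₀.₉₇₅,ₙ₋₁), where T is noncentral t with n−1 degrees of freedom and noncentrality d√n. The protocol gives no value for d, so 0.3 and 0.5 are assumptions.

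| n | critical t | d = 0 | d = 0.3 (noncentrality) | d = 0.5 (noncentrality) |
|---|---|---|---|---|
| 15 | 2.145 | 5% | 19% (1.162) | 44% (1.936) |
| 18 | 2.110 | 5% | 22.5% (1.273) | 51.6% (2.121) |
| 20 | 2.093 | 5% | 25% (1.342) | 56% (2.236) |

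The last entry is 0.5645 before rounding. If changes are uncorrelated between sessions, the chance that at least one of five such techniques is significant on one outcome is 1 − (1 − p)⁵. That is 66% to 76% at d = 0.3 and 94% to 98% at d = 0.5. Positive correlation between sessions would lower these figures.

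**The ANOVA against control.** A simulation used 10,000 runs, six sessions per woman, n = 14 and 20, rest shifts from 0 to 0.75 SD, a correlation of 0.5 between sessions and 0.7 between pre and post values. With no technique effect, the one-way ANOVA rejected in 0.1% to 0.2% of runs on post values and in 5.0% to 5.4% on change, whatever the rest shift. The paired contrast of each intervention's change with the same woman's control-session change stayed at 5.0% to 5.2%.

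**What the pre-session value is worth.** Let r be the within-woman pre-post correlation and σ² the within-woman variance. Residual variance is σ² for post values, 2(1 − r)σ² for change and (1 − r²)σ² for post values adjusted for the pre-session value.

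- Against post values, adjustment removes r²: 25% at r = 0.5 and 49% at r = 0.7.
- Against change, it removes 1 − (1 + r)/2 = (1 − r)/2: 25% at r = 0.5 and 15% at r = 0.7.

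In the simulation at n = 14, with every technique 0.75 SD of the change better than control, ANOVA power was 11% on post values and 45% on change. That gap should not be credited to the pre-session value alone. The simulated variances were 0.5 between women, 0.2 between sessions and 0.3 residual. Residual variance is therefore 1.0 for one-way post values and 0.5 once the pairing within woman is used. With the pre-session value added, within-woman r = 0.2/0.5 = 0.4 and the variance is 0.5 × (1 − 0.16) = 0.42. Most of the loss comes from ignoring the pairing.

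**Power of the control contrast at the planned size.** For a 0.75 SD advantage in change over control, let ρ be the correlation between a woman's two changes. The SD of the difference is √(2(1 − ρ)).

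| ρ | n = 15 | n = 20 |
|---|---|---|
| 0 | 48% | 61% |
| 0.25 | 60% | 74% |
| 0.5 | 77% | 89% |
| 0.75 | 97% | 99% |

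The protocol gives no value for ρ. No multiplicity adjustment is included.

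**The case against.** The strongest reply is that the control comparison is already planned. The ANOVA names control, and section 8 leaves the relative effectiveness of the treatments to the post-hoc step. This stands. It would be wrong to infer that the plan as a whole ignores control, or that techniques will be chosen by counting significant paired tests, because the protocol says neither.

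Second, a reader might infer that the ANOVA discards the pre-session value. The text does not say so. Its dependent variable is open, change is a natural reading after a sentence about changes, and a statistical analysis plan that is not shown could settle it.

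Third, it is tempting to argue that an ANOVA on post values would present rest as a treatment effect. It would not. Control shares the room and the order is random, so the rest shift is in both sides of the comparison. Leaving out the pre-session value costs precision and does not create that bias.

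Fourth, the 19% to 56% are not type I error rates of the paired t-test. Its null is no before-after change, and if rest moves the outcome, rejecting that null is correct. The rates become errors only when the result is taken as evidence for the technique.

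These replies do not remove the mismatch between a hypothesis against control and a lead analysis without control, with no ranking between the analyses.

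**Conclusion.** The point holds in a limited form. The only test that section 8 ties by name to the primary outcomes does not address the primary hypothesis, and the comparison that does address it is not named as decisive. If a before-after change were read as a technique effect, a technique no better than control would pass in 19% to 25% of tests at a rest shift of 0.3 SD and in 44% to 56% at 0.5 SD, for 15 to 20 women. The shifts are assumed, and the calculation takes roughly normal changes and two-sided tests.

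The documents do not support calling this a false-positive rate of the whole plan, nor attributing the bias to the ANOVA. For the ANOVA the issue is only that use of the pre-session value is unstated, with a possible loss of precision that depends on r. A smaller ambiguity goes with it. The two time points for HR, BP and FT probably refer to each session, but section 7 does not say so, and the adjusted contrast needs it.

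**What to change.** Reword section 8 as follows:

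- Make the within-woman contrast of each intervention with the control session the test of the primary hypothesis. Use the post-session value as outcome, adjusted for that session's pre-session value, in one model over all six sessions with participant as random effect.
- Report before-after changes within each condition, control included, as means with confidence intervals and without tests.

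In section 7, state that HR, BP and FT are measured at the start and end of every session, including control.

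The cost is a change of wording. If the physiological measures are indeed taken at each session, the data and software stay the same and no further visits are needed. The sponsor should note that power for the control contrast at 15 to 20 women depends on a correlation that the protocol does not give.

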4.2 Sample size calculation

To estimate the sample size of this pilot study, standard formulas (21) used for calculation are:

$$\text{Sample size (per equal-sized group)} = 16 \times \text{standard deviation} \div (\text{difference})^2$$

Here the effect size and standard deviation (SD) are estimated from a previous research (22), which evaluated the effect of audio-visual imagery on patient anxiety and physiological parameters. A

sample of 51 patients was able to demonstrate a significant reduction in HR (mean change (Z) = -0.75, SD = 1.00; p=0.01). Accordingly, the estimated sample size (per equal-sized group) would be 28. However, since the present study will use a within-subject design, a sample of 14 participants will likely be able to demonstrate changes. Considering the potential drop-off rates, we intend to involve a total of 15-20 subjects in this study.

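### Control is compared with the interventions by a one-way ANOVA on groups, although every mother has all six sessions and the sample of 14 is justified by that within-subject design

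*Protocol*

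**What the plan says.** Section 4 of the protocol sets the design: "A within-subject design will be used to evaluate the effectiveness and participants' feeling towards the five tested interventions compared to a control situation". Section 6 confirms it: "All participants will receive all five treatments and control in random order". Each participant therefore contributes six sessions.

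Section 4.2 takes its inputs from a cited study that found a "reduction in HR (mean change (Z) = -0.75, SD = 1.00; p=0.01". It concludes that "the estimated sample size (per equal-sized group) would be 28", and then that "since the present study will use a within-subject design, a sample of 14 participants will likely be able to demonstrate changes". Planned enrolment is 15 to 20.

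The primary hypothesis in section 3 is set against control: "Compared to the control state, all five relaxation interventions associated with increased perceived relaxation in varying degrees and reduced perceived stress".

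Section 8 gives three analyses: a paired t-test of change from before to after treatment, unspecified post-hoc comparisons, and, for the comparison with control, "One-way ANOVA will be conducted to find differences between control and each intervention group". It names no repeated-measures form, participant term or within-subject factor.

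**The concern.** A one-way ANOVA treats the six conditions as six independent samples. Here they are six measurements on the same mothers. Differences between mothers, which cancel when a mother is compared with herself, stay in the error term. Post-hoc tests built on the same ANOVA inherit that error.

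The paired t-test does not fill the gap. It is valid for change within one condition, but a mother may relax simply by sitting in a quiet room for the session. Change within an intervention session cannot by itself support a claim relative to control.

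At stake is the ability to show that an intervention differs from control. With complete data the condition means and their ranking are the same under either analysis, so a choice made on ranking alone would not change.

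**Working it through.** **Inputs.** Difference 0.75 and SD 1.00 (section 4.2, a heart-rate figure); n=14, enrolment 15 to 20 (section 4.2); six conditions (section 6); 5% level (section 8). Assumed: two-sided testing; 80% power, as the multiplier 16 implies; equal variances; one common within-mother correlation ρ, not given in the protocol and so varied; complete data; 0.75 SD in all five interventions unless stated. Single-contrast powers are unadjusted for multiplicity.

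**Reproducing the plan's figures.** 16 × 1.00 / 0.75² = 16 / 0.5625 = 28.4, the stated 28. Two routes lead to 14:
- A paired contrast with control needs n = 7.85 × 2(1−ρ) / 0.75², which is 13.95 at ρ = 0.5.
- A single before-after change with SD 1.00 needs 7.85 / 0.75² = 13.95.

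The protocol therefore does not fix ρ.

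**The two error terms.** The variance of a mean difference between two conditions is 2σ²(1−ρ)/n. The one-way ANOVA uses 2σ²/n, too large by the factor 1/(1−ρ), which is 2 at ρ = 0.5. Against this, it has 6 × 14 − 6 = 78 error degrees of freedom, and the paired test has 13. Single-contrast power breaks even at ρ of about 0.12 for n=14 and 0.08 for n=20.

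**One contrast with control.** For the one-way ANOVA at n=14 and ρ = 0, the noncentrality is 0.75 × √(14/2) = 1.98, against a critical value of 1.99 on 78 df: 50% power. With 28 per condition (162 df) it is 80%. Paired powers are from the noncentral t with SD of difference √(2(1−ρ)); one-way powers at other ρ are simulated.

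| ρ | n=14, one-way | n=14, paired | n=20, one-way | n=20, paired |
|---|---|---|---|---|
| 0 | 50% | 45% | 65% | 61% |
| 0.1 | 50% | 49% | 66% | 66% |
| 0.3 | 50% | 59% | 68% | 77% |
| 0.5 | 51% | 74% | 71% | 89% |
| 0.7 | 51% | 92% | 75% | 98% |

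At n=15 the figures are 54% against 63% (ρ = 0.3) and 54% against 77% (ρ = 0.5).

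**Overall test** (simulated; RM = repeated-measures ANOVA, GG = with Greenhouse-Geisser correction).

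| ρ | n=14, one-way | n=14, RM uncorrected / GG | n=20, one-way | n=20, RM uncorrected / GG |
|---|---|---|---|---|
| 0 | 44% | 44 / 35% | 62% | 61 / 55% |
| 0.1 | 41% | 48 / 39% | 60% | 67 / 61% |
| 0.3 | 35% | 60 / 51% | 56% | 79 / 75% |
| 0.5 | 28% | 77 / 70% | 50% | 92 / 90% |

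With graded effects of 0.15, 0.30, 0.45, 0.60 and 0.75 SD (assumed) and n=14, one-way against GG is 37% and 29% at ρ = 0, 34% and 32% at 0.1, 27% and 43% at 0.3, and 20% and 60% at 0.5.

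**Type I error and precision, n=14.** The one-way overall test rejects a true null in 5%, 3%, 2%, 1% and 0.2% of trials at ρ = 0, 0.1, 0.2, 0.3 and 0.5. Its intervals for a contrast, relative to paired intervals, are 0.94, 0.99, 1.05, 1.12, 1.32 and 1.70 times as wide at ρ = 0, 0.1, 0.2, 0.3, 0.5 and 0.7.

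**Unequal correlations.** Section 6 says "we combined the guided relaxation tape with lighting and the music tape with lighting as two additional interventions in this study", so the interventions share components and may correlate more with each other than with control. Assume 0.2 between control and interventions and 0.6 among interventions, with n=14. A contrast using one pooled within-mother error then has 10.9% type I error, against 4.9% paired. With 0.3 and 0.7 it is 12.2% against 5.0%. The overall test holds 3.7 to 3.9% with Greenhouse-Geisser and 5.3 to 5.6% with Huynh-Feldt.

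**The case against.** **The sample size may agree with the paired t-test.** Section 4.2 starts from a mean change and speaks of demonstrating changes, and 14 follows from a one-sample before-after calculation. This stands as a reading of where 14 came from, and it means 14 does not imply ρ = 0.5. It does not rescue the comparison with control, which is the stated purpose of the design and the content of the primary hypothesis.

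**The 50% is particular to n=14.** This is correct: the noncentrality there almost equals the critical value. At n=20 the one-way contrast rises with ρ, and the loss at ρ = 0.3 is 9 points. The 80% at 28 per condition is likewise the zero-correlation value; it reaches 88% at 0.5.

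**The loss may be small.** Subtracting the pre-session value removes stable differences between mothers, so ρ for change scores may be low. At ρ near zero the corrected analysis has slightly less power. This limits the size of the problem but does not make six sessions from one mother independent.

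**The authors may have meant a one-way repeated-measures ANOVA, and an analysis plan not at hand may say so.** That is possible, but section 8 names a method and speaks of intervention groups. If the repeated-measures form was meant, a few words settle it.

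**It is a pilot and the error is conservative.** Both are true. They are reasons not to rank this higher, but the pilot is meant to select therapies for a later trial, and an effective one could appear no different from control because of the error term alone.

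**Conclusion.** The concern holds. The stated test against control conflicts with the within-subject design in sections 4 and 6, and it does not use the pairing to which section 4.2 credits the smaller sample.

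At 0.75 SD and n=14, a single contrast loses about 9 points of power at ρ = 0.3 and 23 at ρ = 0.5; the overall test against Greenhouse-Geisser loses 16 and 42. At n=20 the single-contrast losses are 9 and 18 points, the overall ones 19 and 40. At ρ of about 0.1 or below a single contrast loses nothing.

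These sizes rest on an unknown correlation, equal variances, and a heart-rate effect applied to a difference from control. The conservative direction also needs positive correlation: at ρ = −0.15 the one-way overall test rejects a true null in 8.5% of trials. The point should be fixed, but it does not undermine the study.

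**What to change.** Reword section 8 so that:
- the primary hypothesis is tested by the five within-mother intervention-minus-control contrasts of before-after change, each with its own paired standard error and not a pooled within-mother error;
- the post-hoc comparisons between interventions are made in the same way;
- the overall test is a repeated-measures ANOVA with condition (six levels) as within-subject factor and a Greenhouse-Geisser or Huynh-Feldt correction;
- the before-after t-tests within each condition are descriptive and not evidence against control.

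If sessions are missed, a linear mixed model with unstructured covariance within participant is an alternative.

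**Cost.** Protocol wording and a little more analysis in SPSS 24; no new data or visits. If ρ is near zero, power at n=14 falls by about 5 points for one contrast (50% to 45%) and 9 for the overall test with Greenhouse-Geisser (44% to 35%; 42% with Huynh-Feldt). Repeated-measures ANOVA drops a mother with any missing session; a paired contrast drops her only if one of its two sessions is missing. The unstructured model has 6 × 7 / 2 = 21 covariance parameters for 14 to 20 mothers and may not converge. Multiplicity across the five contrasts and several primary outcomes is a separate matter that this change does not settle.

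### The six conditions form a within-mother 2x3 layout (light by sound), but section 8 plans a one-way ANOVA with no mother term and no pooled light or sound contrast

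*Protocol*

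**What the plan says.** Protocol section 4: "A within-subject design will be used to evaluate the effectiveness" of the five interventions against a control situation. Section 5 defines control as no treatment. Section 6 names tape, music and lighting as the three basic interventions, then adds "we combined the guided relaxation tape with lighting and the music tape with lighting as two additional interventions in this study". It also states: "All participants will receive all five treatments and control in random order".

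Section 6.4 gives the purpose of the two combinations: "to find out whether the combined treatment could increase the relaxation level by stimulating vision (lighting) and audition (tape) together".

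Section 8 plans paired t-tests before and after treatment, and then: "One-way ANOVA will be conducted to find differences between control and each intervention group". The follow-up is: "Post-hoc analysis will be used to compare the effectiveness of each treatment". No mother or repeated-measures term, light factor, sound factor or interaction is named.

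Section 3 sets two hypotheses: each of the five interventions does better than control, and the two combinations may do better than the three single treatments. Section 1 gives the ultimate aim as choosing therapies for a later trial.

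**The concern.** A one-way ANOVA of groups is a model for unstructured, independent samples. Here the same mothers supply all six conditions, and the conditions are built from two components.

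Each mother gives three with/without-light pairs (light v control, tape plus light v tape, music plus light v music). She gives two with/without-tape pairs and two with/without-music pairs. The named analysis never brings these pairs together into one estimate. With 15 to 20 mothers, precision is scarce. Whether light adds anything, and how tape compares with music, would help the choice for the next trial.

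**Working it through.** **Inputs.** From the protocol: six conditions per mother (section 6), 15 to 20 mothers, effect 0.75 with SD 1.00 for heart rate (section 4.2), significance at 0.05 (section 8). Assumed: two-sided tests; independent session errors with variance s² once the mother effect is removed; paired-difference SD of 1, so 2s² = 1 and s² = 0.5; n = 18 as a value within the planned range.

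**The protocol's own figures.** 16 × 1.00 / 0.75² = 28.4, in line with the stated 28 per group. For paired data, (1.96 + 0.842)² / 0.75² = 13.95, so 14 as stated. The 14 implies a paired-difference SD of 1, which is why that value is used here.

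**Layout.**

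| | no sound | tape | music |
|---|---|---|---|
| no light | control | tape | music |
| light | light | tape + light | music + light |

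No cell is empty, and each mother fills all six.

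**Variances, with a mother term in the model.**
- One pair of conditions: s²/n + s²/n = 2s²/n.
- Light, mean of three cells minus mean of three cells: s²/3n + s²/3n = (2/3)s²/n. Ratio to one pair: 1/3. SE reduction: 1 − √(1/3) = 42%.
- Tape or music, mean of two cells minus mean of two cells: s²/2n + s²/2n = s²/n. Ratio: 1/2. SE reduction: 1 − √(1/2) = 29%.
- A combination against control under additivity: (2/3 + 1)s²/n = 1.667s²/n against 2s²/n, a saving of only one sixth.

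A simulation at n = 14 agrees: 0.0716 against 0.0236 for light, and 0.0721 against 0.0360 for tape.

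**Power** (noncentral t, 5(n − 1) = 85 df at n = 18; variances 1/18, 0.333/18 and 0.5/18).

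| True effect (paired-difference SD) | One pair | Light, pooled | Tape or music, pooled |
|---|---|---|---|
| 0.4 (assumed) | 39% | 83% | 66% |
| 0.5 (assumed) | 55% | 95% | 84% |
| 0.75 (protocol) | 88% | about 100% | 99% |

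At 0.4 SD with 15 mothers the figures are 33%, 75% and 58%; with 20 they are 43%, 87% and 71%.

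**If the effects do not add.** Let both combinations carry an extra effect g.
- The averaged light effect then differs from light alone by (0 + g + g)/3 = 2g/3. The averaged tape or music effect differs from its simple effect by (0 + g)/2 = g/2.
- As an estimate of light alone, the pooled value loses its mean-squared-error advantage when (2g/3)² exceeds (2 − 2/3)s²/n. At n = 18 this is g = √(1.333 × 0.5/18)/0.667 = 0.29 SD. For tape or music it is g = √(0.5/18)/0.5 = 0.33 SD.
- With the full interaction fitted, the simple effects against control gain nothing.

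**Precision of the interaction.** The contrast is the light effect averaged over tape and music, minus the light effect without sound. Its variance is (4 × 1/4 + 2)s²/n = 3s²/n = 1.5/18, so the SE is 0.289. The 95% half-width is 1.988 × 0.289 = 0.57 SD, and power at 0.4 SD is 28%.

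**What the combination-versus-single contrast shows.** With additive effects L, T and M, the mean of the combinations minus the mean of the singles is L + (T + M)/2 − (L + T + M)/3 = 2L/3 + (T + M)/6. If all three are positive, this is positive without any interaction.

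**The case against.** The strongest reply is that section 8 fits the stated questions. Both hypotheses in section 3 compare cell means, and no objective asks for a light main effect. The planned post-hoc comparisons can include tape plus light against tape and music plus light against music. A six-level model and a 2x3 model with interaction fit the same six means, so the factorial contrasts can be taken from either, and a separate SAP might name them.

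Most of this stands. A reader might infer that the plan throws the information away for good, or that the question in section 6.4 cannot be answered. The documents support neither. The data are collected, and whether a combination raises relaxation can be read from combination-versus-single comparisons. Nor does section 6.4 clearly hypothesise an interaction: its remark that effects might be enhanced through different pathways is compatible with simple addition.

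It is also fair that the efficiency gain needs a small interaction, which this sample can hardly check. Pooling further assumes that the light and music are alike across cells. Mothers choose both (sections 6.2 and 6.3), and the text does not say whether the choice stays fixed between single and combined sessions.

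What does not fall away is the model that section 8 itself fixes: a one-way ANOVA of groups, for a design in which each mother supplies all six conditions. A repeated-measures one-way ANOVA would cure the missing mother term, but it would still leave the light and sound contrasts unpooled unless they were named.

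**Conclusion.** The point holds as a worthwhile improvement at no cost in data. The planned model does not match the within-mother 2x3 layout. Even with a mother term, one pairwise comparison carries as little as one third of the information on light and one half of that on tape or music. Those shares assume independent session errors and roughly additive effects.

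The power gain depends on the assumed effect: large at 0.4 to 0.5 SD, modest at the protocol's 0.75, where the pairwise comparison already has 88% with 18 mothers. These powers presume that the mother effect has been removed, so they do not measure what is lost by omitting the mother term. That is a separate defect.

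A reader might conclude that component effects should replace the comparisons with control, or settle which techniques go forward. That is not supported. The hypotheses concern the individual conditions, and an interaction known only to about ±0.57 SD cannot establish that the averaged effects represent the simple ones.

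**What to change.** In section 8, replace the one-way ANOVA with a within-mother model, with mother as a blocking or random factor and terms for light, sound and light by sound. From that model:

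- Keep each condition's difference from control, and the combination-versus-single comparisons, as the answers to the stated hypotheses.
- Also report the light effect averaged over the three sound levels, and the tape and music effects averaged over both light levels.
- Report the light-by-sound interaction as an estimate with 95% CI, not as a test that decides which effects are shown.
- State that component effects are supporting evidence for selection and not its sole basis.

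The cost is one paragraph, with the same sessions, data and software. The downside is that averaged effects depart from the simple effects when there is an interaction (by 2g/3 for light and g/2 for tape or music). Both must therefore be shown side by side, with the imprecision of the interaction acknowledged.
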